**Expedited AE reporting timelines are defined as:**

- “24-Hour; 3 Calendar Days” - The AE must initially be reported within 24 hours of learning of the AE, followed by a complete expedited report within 3 calendar days of the initial 24-hour report.
- “7 Calendar Days” - A complete expedited report on the AE must be submitted within 7 calendar days of learning of the AE.

Serious adverse events that occur more than 30 days after the last administration of investigational agent/intervention and have an attribution of possible, probable, or definite require reporting as follows:

**Expedited 24-hour notification followed by complete report within 3 calendar days for:**

- All Grade 3, 4, and Grade 5 AEs

**Expedited 7 calendar day reports for:**

- Grade 2 AEs resulting in hospitalization or prolongation of hospitalization

 For studies using PET or SPECT IND agents, the AE reporting period is limited to 10 radioactive half-lives, rounded UP to the nearest whole day, after the agent/intervention was last administered. Footnote “1” above applies after this reporting period.

Effective Date: May 5, 2011

**Special Instructions:**

- Follow site-specific reporting guidelines.
- Submit the Adverse Event Expedited Report Form to the SAE Coordinator email [REDACTED] The SAE Coordinator will forward to Ono at [REDACTED] within 24 hours of receiving.
- The SAE Coordinator will forward to IND Coordinator [REDACTED] as appropriate. The IND Coordinator will assist the sponsor-investigator in notifying the FDA if required.

**8.5 Other Required Reporting**

8.5.1 Unanticipated Problems Involving Risks to Subjects or Others (UPIRTSOS) in general, include any incident, experience, or outcome that meets **all** of the following criteria:

1. Unexpected (in terms of nature, severity, or frequency) given (a) the research procedures that are described in the protocol-related documents, such as the IRB-approved research protocol and informed consent document; and (b) the characteristics of the subject population being studied;
2. Related or possibly related to participation in the research (in this guidance document, possibly related means there is a reasonable possibility that the incident, experience, or outcome may have been caused by the procedures involved in the research); and
3. Suggests that the research places subjects or others at a greater risk of harm (including physical, psychological, economic, or social harm) than was previously known or recognized.

Some unanticipated problems involve social or economic harm instead of the physical or psychological harm associated with adverse events. In other cases, unanticipated problems place subjects or others at increased *risk* of harm, but no harm occurs.

8.5.2 Submit via appropriate Case Report Forms the following AEs experienced by a patient and not specified in Section 8.5:

8.5.2.1 Grade 1 and 2 AEs deemed *possibly, probably, or definitely* related to the study treatment or procedure.

8.5.2.2 Grade 3 and 4 AEs regardless of attribution to the study treatment or procedure

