## Definitions

### *Adverse Event*

Any untoward medical occurrence associated with the use of a drug in humans, whether or not considered drug related.

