**FDA REPORTING REQUIREMENTS FOR SERIOUS ADVERSE EVENTS (21 CFR Part 312)**

**NOTE:** Investigators **MUST** immediately report to the sponsor **ANY** Serious Adverse Events, whether or not they are considered related to the investigational agent(s)/intervention (21 CFR 312.64)

An adverse event is considered serious if it results in **ANY** of the following outcomes:

- 1) Death
- 2) A life-threatening adverse event
- 3) An adverse event that results in inpatient hospitalization or prolongation of existing hospitalization for  $\geq$  24 hours
- 4) A persistent or significant incapacity or substantial disruption of the ability to conduct normal life functions
- 5) A congenital anomaly/birth defect.
- 6) Important Medical Events (IME) that may not result in death, be life threatening, or require hospitalization may be considered serious when, based upon medical judgment, they may jeopardize the patient or subject and may require medical or surgical intervention to prevent one of the outcomes listed in this definition. (FDA, 21 CFR 312.32; ICH E2A and ICH E6).

**ALL SERIOUS** adverse events that meet the above criteria **MUST** be immediately reported to the sponsor within the timeframes detailed in the table below.

Hospitalization	Grade 1 and Grade 2 Timeframes	Grade 3-5 Timeframes
Resulting in Hospitalization $\geq$ 24 hrs	7 Calendar Days	24-Hour; 3 Calendar Days
Not resulting in Hospitalization $\geq$ 24 hrs	Not required	

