8.5.2.3 Grade 5 AEs (Deaths)

8.5.2.3.1 Any death within 56 days after registration on the trial must be submitted as a Grade 5 AE, with a CTCAE type and attribution assigned.

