## 12.0 Treatment Evaluation Criteria

The ordinal scale used for assessment of the clinical and respiratory status on each day of the study is included below. Each day, the worst (i.e., highest ordinal) score from the previous day will be recorded, i.e., on Day 3, the highest ordinal score from Day 2 is obtained and recorded for Day 2. The scale is as defined by the WHO as follows:

Patient State	Descriptor	Score
Uninfected	No Clinical or Virological Evidence of Infection	0
Ambulatory	No Limitation of activities	1
	Limitation of activities	2
Hospitalized, Mild Disease	Hospitalized, no oxygen therapy	3
	Oxygen by mask or nasal prongs	4
Hospitalized, Severe Disease	Non-invasive ventilation or high flow oxygen	5
	Intubation and Mechanical Ventilation	6
	Ventilation + additional organ support-pressors, RRT, ECMO	7
Dead	Death	8

In addition, patients will be stratified at baseline based on the ordinal scale below. A score of 3-4 is associated with hospitalized with mild disease versus score of 5 is associated with severe disease.

The primary outcome assessment for efficacy will be evaluated based on the number of patients who are alive AND respiratory failure-free at Day 28 after study entry.

Respiratory failure at Day 28 will be defined by clinical diagnosis of respiratory failure corresponding to a score of 5-8 on the above ordinal scale at Day 28. Specifically, respiratory failure is defined by meeting any of the following criteria:

- Requiring ICU admission,
- mechanical ventilation,
- ECMO,
- non-invasive ventilation,
- or high flow oxygen devices,

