**5. Length of Stay:** Length of stay will be defined as the time from study entry until the time of hospital discharge and the number of days hospitalized will be compared between groups by use of non-parametric Wilcoxon rank-sum test. The proportions of patients who require an ICU admission will be compared between randomized groups by the use of independent samples Z-test for proportions and a 95% confidence interval will be constructed for the difference between groups. In addition, time in the ICU will be described in number of days spent receiving ICU care, if applicable.

**6. Duration of Mechanical ventilation / ECMO:** Duration of ventilator / ECMO use will be summarized by medians or quartiles by arm for those subjects who have a baseline score of 6-7 at study entry.

**7. Duration of non-invasive ventilation / high-flow oxygen:** Duration of non-invasive ventilation / high-flow oxygen will be summarized by medians and quartiles by arm for those patients who have a clinical status score of 5 at study entry.

**8. Duration of supplemental oxygen use:** Duration of supplemental oxygenation use will be summarized by medians and quartiles by arm for those patients who have a clinical status score greater than or equal to 4 at study entry.

**9. Occurrence of adverse events related to treatment:** Analyses for safety will include all participants who are randomized and received at least 1 dose of study treatment.

Participants will be grouped according to the treatment to which they were randomized. Events will be summarized on the basis of the date of onset for the event. The maximum grade for each type of adverse event will be recorded for each patient. Frequency tables of adverse events will be constructed based on maximum grade for each treatment arm. Overall adverse event rates, rates of grade 3 or higher events and serious adverse events will be compared between treatment groups using Chi-square or Fisher's exact test.

**10. Development of thrombosis / bleeding complications:** Incidence of arterial and venous thrombosis or bleeding complications will be described and compared by treatment arms by use of chi-square or Fisher's exact test.

Subgroup analyses for the primary and secondary analyses will examine the treatment effect across the following subgroups of interest. Forest plots with odds ratio and 95% confidence intervals will be presented along with interaction tests.

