### 13.6 Sample Size

Randomization will be done according to a 1:1 ratio. Based on data from Wang et al, 82% of patients treated with Remdesivir were alive and free from respiratory failure at day 28. In the preliminary report of Remdesivir for the treatment of COVID-19 in 1059 hospitalized patients, approximately 70% of patients treated with Remdesivir were alive and free from respiratory failure at Day 15; Day 28 data are not yet available. Using an expected proportion of 80% for the SOC control arm, this study would require 132 patients in each arm (total of 264 patients). Sample sizes of 132 in each arm achieves 80% power to detect a difference between the group proportions of 12% for the primary endpoint. The proportion in the treatment arm is assumed to be 80% under the null hypothesis and 92% under the alternative hypothesis. The proportion in the SOC arm is 80%. The test statistic used is the two-sided Z-Test with unpooled variance. The significance level of the test is 0.05 (two-sided).

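### As its text stands, the general toxicity comparison in Section 13.5 item 9 pools deaths and disease-related severe events with other adverse events, so efficacy can offset, or disease events dilute, a camostat toxicity signal in those pooled tests

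*Combined protocol and SAP*

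**What the plan says.** **Collection.** The definitions in Section 8.0 make an AE "Any untoward medical occurrence associated with the use of a drug in humans, whether or not considered drug related". Section 8.5.2.2 asks for "Grade 3 and 4 AEs regardless of attribution to the study treatment or procedure". Grade 1 and 2 events are collected only if at least possibly related (8.5.2.1). Section 8.5.2.3.1 adds: "Any death within 56 days after registration on the trial must be submitted as a Grade 5 AE", with a CTCAE type and an attribution. The serious criteria in Section 8.4 include death, life-threatening events and "An adverse event that results in inpatient hospitalization or prolongation of existing hospitalization for" at least 24 hours. No section exempts or flags progression of COVID-19.

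**Analysis.** Item 9 carries a heading in both 13.3.2 and 13.5 that confines it to treatment-related events. The text beneath applies no such limit: "Overall adverse event rates, rates of grade 3 or higher events and serious adverse events will be compared between treatment groups", by chi-square or Fisher's exact test. Section 13.1 also plans an interim look at AE differences between arms, again with no filter stated.

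**Efficacy endpoint.** Section 12.0 defines respiratory failure as a "clinical diagnosis of respiratory failure corresponding to a score of 5-8 on the above ordinal scale" at Day 28. Score 8 is death; scores 5 to 7 cover non-invasive ventilation or high-flow oxygen up to ventilation with organ support. On the assumed rates, Section 13.6 states: "The proportion in the treatment arm is assumed to be 80% under the null hypothesis and 92% under the alternative hypothesis". The control arm is set at 80%.

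**The concern.** Objective 2.2.7 is to compare safety and toxicity between arms. If item 9 is run as its text reads, some of the events it counts are also events that the primary endpoint counts as failures. The pooled rate then carries efficacy and toxicity together, with three possible consequences for that test:

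- If camostat works, fewer deaths and respiratory failures on camostat offset an excess of drug-caused events.
- If camostat works and adds no toxicity, the comparison can come out significantly in its favour and only restate the efficacy result.
- If camostat does not work, disease events common to both arms add noise and reduce the power to see a toxicity excess.

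**Working it through.** **1. The plan's own figure.** For 80% vs 92%, two-sided 5%, 80% power, the pooled-variance formula gives 131 per arm and the unpooled formula gives 128. At 132 per arm, power is 80.6% (pooled) or 81.4% (unpooled). The stated 132 is consistent with its inputs, so the design rates can be carried forward.

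**2. Disease events implied by the design.** Primary failures are 20% × 132 = 26.4 patients on placebo and 8% × 132 = 10.6 on camostat. If each is reported as a grade 3+ AE, a gap of about 15.8 patients (12 points) enters the pooled comparison in camostat's favour.

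**3. Toxicity that this gap would offset.** Let f be the failure rate, b the background rate of other grade 3+ events in both arms, and t the rate of camostat-caused grade 3+ events, all independent. The share of patients with any grade 3+ event is 1 − (1−f)(1−b)(1−t). The arms are equal when 0.80 = 0.92(1−t), so t = 1 − 0.80/0.92 = 13.0%, whatever b is. With half the planned effect (14% failures on camostat), t = 1 − 0.80/0.86 = 7.0%.

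**4. Effect on the test.** The documents give no rates for other grade 3+ events. I assume 15% on placebo and 25% on camostat, which is t = 1 − 0.75/0.85 = 11.8%. The last column is the exact binomial probability that a two-sided 5% Pearson chi-square, 132 per arm, is significant with camostat worse.

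| What is counted | Placebo | Camostat | Excess detected |
|---|---|---|---|
| Other events only | 15% | 25% | 53% |
| Plus all primary failures, independent | 1 − 0.85×0.80 = 32.0% | 1 − 0.75×0.92 = 31.0% | 1.7% |
| Plus all primary failures, no overlap | 35% | 33% | 1.1% |
| Plus all primary failures, maximal overlap | 20% | 25% | 16% |
| Plus deaths only (assumed 10% vs 4%) | 1 − 0.85×0.90 = 23.5% | 1 − 0.75×0.96 = 28.0% | 13% |
| Plus all primary failures, no efficacy (20% both) | 32.0% | 1 − 0.75×0.80 = 40.0% | 27% |

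With other events at 15% in both arms and the planned efficacy, the rates are 32.0% and 1 − 0.85×0.92 = 21.8%. The test is then significant in camostat's favour 47% of the time.

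**5. Smaller toxicities.** Testing other events alone, 15% vs 20% is detected 19% of the time and 15% vs 17% only 6%. At this background rate, excluding disease events does not make the comparison sensitive to modest excesses.

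**The case against.** The strongest objection is the item 9 heading. If it governs, deaths and respiratory failure judged unrelated drop out and the mixing largely disappears. That stands as an ambiguity, but it does not settle the matter. The text below the heading refers to overall rates and names no filter. Elsewhere the plan states an attribution limit when it wants one, as for grade 1 and 2 collection (8.5.2.1) and the stopping rule (13.7).

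The overlap with the primary endpoint is also inexact. No section names respiratory failure as an AE; its inclusion follows from the definitions and the lack of an exemption. The endpoint is status at Day 28, whereas AEs accrue over time and deaths are counted to Day 56. Section 3.1.6 sets no upper score, so a patient entering at 5 or above may fail with no new AE. These points change the size, and they are why the deaths-only row matters: it shows attenuation, not cancellation.

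The assumed 10-point excess is large. Section 11.1.7 gives its quantified toxicities as below 0.5% each, and the four it calls clinically significant have no incidence. An all-cause comparison is also a defensible choice, because it avoids attribution error.

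A reader might infer that camostat toxicity would go unseen, or that item 9 holds the only between-arm safety tests. The documents do not support either. Item 10 tests thrombosis and bleeding, and item 2 gives death its own log-rank test and Day 28 and 56 rates. Tables by event type and maximum grade are planned, attribution is recorded, the stopping rule counts at least possibly related events separately by arm, and a DSMB reviews safety data.

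**Conclusion.** The concern holds for the pooled overall, grade 3+ and SAE comparisons in item 9, read as the text stands. Inclusion of deaths is explicit; inclusion of respiratory failure is inferred.

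At the design effect, and if every primary failure is also a grade 3+ AE, the benefit would offset a 13.0% camostat-caused toxicity. On the assumed 15% vs 25%, detection falls from 53% to about 2% (1% to 16% across the range of overlap), to 13% with deaths only, and to 27% with no efficacy. These figures depend on the assumed rates and on how many failures are reported as AEs; if fewer are reported, the offset is smaller. They describe one set of formal tests, not the whole safety evaluation. The point deserves correction because the heading and text of item 9 conflict and the remedy is cheap.

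**What to change.** 1. In item 9 of 13.3.2 and 13.5, reconcile the heading with the text by stating whether an attribution filter applies to the between-arm comparison.
2. Prespecify the grade 3+ and SAE comparisons twice: for all events, and excluding deaths from COVID-19 and respiratory-failure or other primary-endpoint component events. Present the two side by side.
3. Identify the excluded events blind to treatment arm, either from the CTCAE term and attribution already collected or from one added CRF flag.

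The cost is one extra row in the safety tables and, if chosen, one CRF field. AE and SAE reporting does not change, and all-cause death keeps its existing analysis. The downside is that a drug-related respiratory event could be classed as progression and leave the restricted comparison, which is why the all-event rates must stay beside it.

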8.5.2.3 Grade 5 AEs (Deaths)

8.5.2.3.1 Any death within 56 days after registration on the trial must be submitted as a Grade 5 AE, with a CTCAE type and attribution assigned.

## 8.6 Pregnancy

The investigator should report all pregnancies, including those of partners of male patients, within 24 hours to ACCRU at [REDACTED] The SAE Coordinator will forward to Ono at [REDACTED] within 24 hours of being notified.

Prior to obtaining private information about a pregnant woman and her infant, the investigator must obtain consent from the pregnant woman and the newborn infant's parent or legal guardian before any data collection can occur. A consent form will need to be submitted to the IRB for these subjects if a pregnancy occurs. If informed consent is not obtained, no information may be collected.

*In cases of fetal death, miscarriage or abortion the mother is the patient. In cases where the child/fetus experiences a serious adverse event other than fetal death, the child/fetus is the patient.*

NOTE: When submitting ACCRU Adverse Event Report reports for "Pregnancy", "Pregnancy loss", or "Neonatal loss", the potential risk of exposure of the fetus to the investigational agent(s) should be documented in the "Description of Event" section. Include any available medical documentation.

## 9.0 Biospecimens

### 9.1 Summary Table of Research Blood/Blood Products to Be Collected for This Protocol

	Specimen Purpose	Mandatory or Optional	Blood or Body Fluid being Collected	Type of Collection Tube (color of tube top)	Volume to collect per tube (# of tubes to be collected)	Day 1	Day 7	Day 14	Day 28	Day 56	Process at site? (Yes or No) 
-C1	 Correlative  Banking	Mandatory on day 1, optional all other days	Nasal Pharyngeal	Swab	1	X	X	X	X	X	N
-C2	 Correlative  Banking	Mandatory on day 1, optional all other days	Whole blood	SST (red and black marble top)	8.5mL (1)	X	X	X	X	X	N
C3 	 Correlative  Banking	Mandatory on day 1, optional all other days	Stool	Brown and white bottle	25mL	X	X	X	X		N
-C4	 Correlative  Banking	Mandatory on day 1, optional all other days	Saliva	Oragene	1	X	X	X	X		N

	Specimen Purpose	Mandatory or Optional	Blood or Body Fluid being Collected	Type of Collection Tube (color of tube top)	Volume to collect per tube (# of tubes to be collected)	Day 1	Day 7	Day 14	Day 28	Day 56	Process at site? (Yes or No) 
-C5	 Correlative  Banking	Mandatory on day 1, optional all other days	PBMC, plasma	Na Heparin (green top)	10mL	X				X	N

1. All samples will be processed and stored by Arizona BAP.
2. All Mayo sites using RLIMS must add MCA processing instructions to RLIMS builds.
3. Stool samples can be  $\pm$  1 day and will be collected only if patient is able to produce.

## 9.2 Kits will be used for this study.

9.2.1 Kits will be supplied by the MCA Biospecimen Accessioning and Processing Shared Resource (BAP).

NOTE: Mayo Clinic Florida BAP will assemble the kits for specimen collection at Mayo Clinic Florida.

9.2.2 The kit contains supplies and instructions for collecting, processing and shipping specimens.

9.2.3 Participating institutions may obtain kits by emailing the Supply Order Form to the number listed on the form (D: ARZ Biobank). Because we are charged for all outgoing kits, a small, but sufficient, supply of the specimen collection kits should be ordered prior to patient entry. **Supply Order Forms must be filled in completely and legibly for quick processing.**

9.2.4 Kits will be sent via Fed Ex® Ground at no additional cost to the participating institutions. **Allow at least two weeks to receive the kits.**

9.2.5 Kits will not be sent via rush delivery service unless the participating institution provides their own Fed Ex® account number or alternate billing number for express mail. **Cost for rush delivery of kits will not be covered by the study.**

[figure not shown]
9.2.6 **Specimens must be collected and shipped Monday – Thursday ONLY. MCA may collect Monday-Friday. Specimens that are drawn during the evening hours (Monday through Wednesday) can be shipped the next morning.**

## 9.3 Shipping Specimens

- 9.3.1 Verify ALL section of the Blood Specimen Submission Form (see Forms Packet), BAP Requisition Form (provided in kit), and specimen collection labels are completed and filled in correctly.
- 9.3.2 Specimens must be shipped the same day they are drawn/collected.  
  
NOTE: Mayo Clinic Florida will process and store specimens at Mayo Clinic Florida Biobank and then ship specimens in batch to Mayo Clinic Arizona at the end of study enrollment.
- 9.3.3 Ship all samples via Priority Overnight service. The nasal pharyngeal swabs, saliva, Na Heparin, SST tubes and brown and white stool bottles will be shipped in a dual-temperature shipping container. Place the refrigerated SST red and black marble top and the brown and white stool container with a properly prepared cold pack in one compartment. See kit instructions for specific details for cold pack preparation (i.e., frozen or refrigerated) and proper packing of blood and cold pack to avoid freezing of specimen. Place the nasal pharyngeal swab, Oragene saliva samples, and NA Heparin green top tube with an ambient cool pack in the other compartment of the dual-temperature shipping container.
- 9.3.4 Ship specimens via Priority Overnight service. **Do not send samples on weekends or just prior to federal holidays.**
- 9.3.5 The BAP kits will include a smart shipper label (3x5 white barcoded label) affixed to the shipping boxes. The smart shipper label is a pre-addressed return label, which replaces the need for an airbill. Shipping costs will be covered by the funding sponsor if the shipping box provided with the BAP kit is used for shipping specimens to BAP Receiving.

Recipient Name: BAP  
 Company Name: Mayo Clinic  
 Address Line 1: [name]  
 Address Line 2: [name]  
 City: Phoenix  
 State: AZ  
 Zip: 85054  
 [contact]

- 9.3.6 BAP Arizona will receive the samples, accession and process and store the samples as indicated at MCA BAP. Samples will be processed and stored per the protocol and then sent weekly in batches to:

